5. STUDY POPULATION

The study population will consist of patients who are currently receiving or have previously received durvalumab monotherapy or durvalumab in combination with any other approved or investigational anticancer agents, in a parent clinical study. Patients enrolled on a control arm in a parent study are not eligible.

At enrollment, informed consent to participate in the study will be obtained from all patients, and eligible patients will be enrolled in Cohorts 1, 2 or 3, according to their treatment status. There are 2 consent forms that will be signed by the patient based on whether the patient is on treatment or starting retreatment (treatment informed consent form [ICF]) or off treatment (follow-up ICF). All patients in Cohort 1 must sign the treatment ICF. The follow-up ICF will be used for patients who enroll in Cohort 3. Cohort 2 patients who will be eligible for future retreatment with durvalumab must sign the follow-up ICF at enrollment, then must agree to

reconsenting under the treatment ICF to start retreatment, and must meet the eligibility criteria detailed in Sections 5.1 and 5.2.

- Cohort 1: includes patients who received durvalumab monotherapy or durvalumab combination therapy under the parent clinical study (including those undergoing retreatment per the parent study) who have not clinically progressed and who are eligible to continue durvalumab treatment after completing dosing of all other anticancer agents, including other investigational agents, which are a formal component of the parent study. If a patient was already retreated with durvalumab in the parent clinical study and has not progressed while on treatment, then they would be potentially eligible to enter Cohort 1; a combination treatment course initiated in the parent clinical study must be completed prior to study entry.
- Cohort 2: includes patients who completed durvalumab monotherapy or in combination with any other approved or investigational anticancer agents in a parent study, without confirmed PD during the period of treatment, and who are potentially eligible for retreatment with durvalumab. The patient should not have received any other approved or investigational anticancer agents since completion of durvalumab treatment. Patients who completed the prespecified duration of treatment with durvalumab in a parent clinical study, who received clinical benefit and then subsequently experienced confirmed PD after completion of planned treatment, will be permitted to restart durvalumab treatment provided they meet the eligibility criteria. If a patient was already retreated with durvalumab in the parent clinical study and retreatment has ended, they are no longer eligible for retreatment in this study.
- Cohort 3: includes patients previously treated with durvalumab monotherapy or in combination with any other approved or investigational anticancer agents who are no longer receiving durvalumab and are not eligible to receive retreatment.

Prospective approval of protocol deviations to recruitment and enrollment criteria, also known as protocol waivers or exemptions, is not permitted.

Each patient should meet all of the inclusion criteria and none of the exclusion criteria for this study, to be assigned to a study cohort. Under no circumstances can there be exceptions to this rule. Patients who do not meet the entry requirements are screen failures, refer to Section 5.4.

For procedures for withdrawal of incorrectly enrolled patients see Section 7.3.

5.1 Inclusion criteria

Patients are eligible to be included in the study only if all of the following inclusion criteria and none of the exclusion criteria apply:

General inclusion criteria for all patients:

1. Patient must be 18 years or older, at the time of signing the ICF. For subjects aged <20 years and enrolled in Japan, a written ICF should be obtained from the subject and his

or her legally acceptable representative.

2. Patient received durvalumab monotherapy and/or durvalumab containing combination in an AstraZeneca/MedImmune-sponsored parent clinical study that is approved for enrollment into this study.
3. Patients who received durvalumab in combination with any other approved or investigational anticancer agents in the parent clinical study must have completed or discontinued all other anticancer therapy (beyond durvalumab regimen).
4. Patient must be willing and able to provide written informed consent and to comply with scheduled visits and other study procedures.

Additional inclusion criteria for patients entering Cohort 1:

5. Currently receiving durvalumab monotherapy (this includes patients enrolled in durvalumab combinations who have completed or discontinued all other anticancer therapy combined with durvalumab in the parent clinical study, and are now receiving durvalumab monotherapy), and is currently benefiting from treatment with durvalumab therapy, as determined by the Investigator.

Additional inclusion criteria for patients entering Cohort 1 and Cohort 2:

6. Adequate organ function as defined below:
 - (a) Serum bilirubin $\leq 1.5 \times$ the upper limit of normal (ULN). This will not apply to patients with confirmed Gilbert's syndrome, who will be allowed in consultation with their physician.
 - (b) Alanine aminotransferase (ALT) and aspartate aminotransferase (AST) $\leq 2.5 \times$ ULN; for patients with hepatic metastases, ALT and AST $\leq 5 \times$ ULN.
 - (c) Measured creatinine clearance (CL) >40 mL/min or calculated CL >40 mL/min as determined by Cockcroft-Gault (using actual body WT)

Males:

$$\text{Creatinine CL (mL/min)} = \frac{\text{Weight (kg)} \times (140 - \text{Age})}{72 \times \text{serum creatinine (mg/dL)}}$$

Females:

$$\text{Creatinine CL (mL/min)} = \frac{\text{Weight (kg)} \times (140 - \text{Age})}{72 \times \text{serum creatinine (mg/dL)}} \times 0.85$$

7. Evidence of postmenopausal status or negative urinary or serum pregnancy test for female premenopausal patients. Women will be considered postmenopausal if they have been amenorrheic for 12 months without an alternative medical cause. The following age-specific requirements apply:

- (a) Women <50 years of age would be considered postmenopausal if they have been amenorrheic for 12 months or more following cessation of exogenous hormonal treatments and if they have luteinizing hormone and follicle-stimulating hormone levels in the postmenopausal range for the institution.
 - (b) Women ≥ 50 years of age would be considered postmenopausal if they have been amenorrheic for 12 months or more following cessation of all exogenous hormonal treatments, had radiation-induced menopause with last menses >1 year ago, had chemotherapy-induced menopause with last menses >1 year ago.
 - (c) Women who are surgically sterile (eg, bilateral salpingectomy, bilateral oophorectomy, or complete hysterectomy) are eligible.
8. World Health Organization (WHO)/Eastern Cooperative Oncology Group (ECOG) performance status (PS) of ≤ 2 at enrollment

Additional inclusion criteria for retreatment patients in Cohort 2

9. Received durvalumab in a parent clinical study that is approved to enroll into this study.
10. Completed the defined treatment duration with durvalumab monotherapy or durvalumab combination therapy in the parent clinical study, as defined below:
- (a) Previously benefited from treatment with durvalumab monotherapy or durvalumab combination therapy, as determined by the Investigator.
 - (b) Has not previously received retreatment with durvalumab monotherapy.
 - (c) Maintained SD or better (Response Evaluation Criteria in Solid Tumors version 1.1 [RECIST v1.1]) throughout the period of defined treatment duration, and has not received any subsequent anticancer therapy.
11. At least 1 lesion that can be accurately measured at baseline as ≥ 10 mm in the longest diameter (except lymph nodes which must have a short axis ≥ 15 mm) with computed tomography (CT) or magnetic resonance imaging (MRI), and that is suitable for accurate repeated measurements as per RECIST v1.1 guidelines.

5.2 Exclusion criteria

Patients must not enter the study if any of the following key exclusion criteria are fulfilled:

1. Involvement in the planning and/or conduct of the study (applies to both AstraZeneca staff and/or staff at the study site).

Additional exclusion criteria for Cohort 1 and Cohort 2:

2. Currently receiving treatment in another interventional clinical study other than a parent clinical study, or received treatment during the follow-up period before retreatment (Cohort 2 only).

3. Experienced an immune-mediated or non-immune-mediated (hematologic and non-hematologic) toxicity that led to permanent discontinuation of durvalumab in the parent clinical study.
4. Any unresolved toxicity National Cancer Institute (NCI) Common Terminology Criteria for Adverse Events (CTCAE) Grade ≥ 2 from previous anticancer therapy with the exception of alopecia, vitiligo, and the laboratory values defined in the inclusion criteria.
5. Prior treatment with immunotherapy other than durvalumab, or any other approved or investigational anticancer agents other than MedImmune/AstraZeneca's investigational immunotherapy molecules administered in the parent clinical study.
6. Any concurrent chemotherapy, investigational product (IP), biologic or hormonal therapy for cancer treatment. Concurrent use of hormonal therapy for non-cancer-related conditions (eg, hormone replacement therapy) is acceptable.
7. Active or prior documented autoimmune or inflammatory disorders (including inflammatory bowel disease [eg, colitis or Crohn's disease], diverticulitis [with the exception of diverticulosis], systemic lupus erythematosus, Sarcoidosis syndrome, or Wegener syndrome [granulomatosis with polyangiitis, Graves' disease, rheumatoid arthritis, hypophysitis, uveitis, etc]). The following are exceptions to this criterion:
 - (a) Patients with vitiligo or alopecia.
 - (b) Patients with hypothyroidism (eg, following Hashimoto syndrome) stable on hormone replacement.
 - (c) Any chronic skin condition that does not require systemic therapy.
 - (d) Patients without active disease in the last 5 years may be included but only after consultation with the Study Physician.
 - (e) Patients with celiac disease controlled by diet alone.
8. History of allogenic organ transplantation.
9. Uncontrolled intercurrent illness, including but not limited to, ongoing or active infection, symptomatic congestive heart failure, uncontrolled hypertension, unstable angina pectoris, uncontrolled cardiac arrhythmia, active ILD, serious chronic GI conditions associated with diarrhea, or psychiatric illness/social situations that would limit compliance with study requirement, substantially increase risk of incurring AEs or compromise the ability of the patient to give written informed consent.
10. Documented active infection including tuberculosis (clinical evaluation that includes clinical history, physical examination and radiographic findings, and tuberculosis testing in line with local practice), hepatitis B virus (HBV) (known positive HBV surface antigen [HbsAg] result), hepatitis C virus (HCV), or human immunodeficiency virus (HIV) (positive HIV 1/2 antibodies). Patients with a past or resolved HBV infection (defined as the presence of hepatitis B core antibody and absence of HbsAg) are eligible. Patients positive for HCV antibody are eligible only if polymerase chain reaction is negative for HCV RNA. Prior HIV and HBV/HCV testing from the parent

clinical study is acceptable documentation and patients will not need to undergo an additional testing prior to Cohort 1 enrollment in this study. For Cohort 2 patients, prior HIV testing from the parent clinical study is acceptable documentation and patients will not need to undergo an additional test prior to retreatment. However, patients will require retesting for HbsAg and HCV within the 28-day window prior to retreatment.

11. Receipt of live attenuated vaccine within 30 days prior to the first dose of study drug in the present study. Note: Patients, if enrolled, should not receive live vaccine while receiving study drug and up to 90 days after the last dose of study drug.
12. Female patients who are pregnant or breastfeeding, or male or female patients of reproductive potential who are not willing to employ effective birth control from screening to 90 days after the last dose of durvalumab monotherapy or 180 days after the last dose of durvalumab + tremelimumab combination.
 - Highly effective methods of contraception are defined as one that results in a low failure rate (eg, less than 1% per year) when used consistently and correctly. Note that some contraception methods are not considered highly effective (eg, male or female condom with or without spermicide; female cap, diaphragm, or sponge with or without spermicide; non-copper containing intrauterine device; progestogen-only oral hormonal contraceptive pills where inhibition of ovulation is not the primary mode of action [excluding Cerazette/desogestrel which is considered highly effective]; and triphasic combined oral contraceptive pills).
 - For patients randomized to receive SoC treatment in parent protocols, follow the local prescribing information relating to contraception, the time limit for such precautions, and any additional restrictions for agents in the SoC treatment regimen.
13. Diagnosis of a new primary malignancy since enrollment into the parent clinical study, with the exception of adequately treated non-melanomatous skin cancer and carcinoma in situ with no evidence of disease.
14. Must not have required the use of additional immunosuppression other than corticosteroids for the management of an AE >Grade 1, have not experienced recurrence of an AE if re-challenged, and not currently require maintenance doses of >10 mg prednisone or equivalent per day.
15. Known allergy or hypersensitivity to any of the study drugs or any of the study drug excipients.

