2. INTRODUCTION

2.1 Study rationale

This is a multicenter, open-label, global study that will enroll patients who are currently receiving durvalumab monotherapy, or have previously received durvalumab as monotherapy or in combination with any other approved or investigational anticancer agents, in an eligible AstraZeneca/MedImmune-sponsored clinical study (herein referred to as a parent clinical study).

The aims of the study are the following:

- To collect long-term safety and survival data from patients who received durvalumab monotherapy and/or durvalumab in combination with any other approved or investigational anticancer agents.
- To provide continued access to durvalumab monotherapy until confirmed progressive disease (PD) to patients currently receiving treatment.
- To allow for future retreatment with durvalumab monotherapy upon disease progression in patients who previously benefited from treatment with durvalumab as monotherapy, and/or durvalumab in combination with any other approved or investigational anticancer agents and experienced disease progression after completion of planned treatment.

The primary aim of this study is to monitor the long-term safety of durvalumab. Extensive safety-related data are being collected throughout the course of drug development, and knowledge about a drug's safety profile continually evolves as safety data accumulate. This study is aligned with the growing interest in larger, simpler trials to obtain outcome data, including long-term effects of drugs and comparative effectiveness and safety.

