2.3.1 Overall benefits

As is commonly the case for clinical trials with a fixed treatment or study duration, long-term safety and efficacy endpoints often lack feasibility within the time frame permitted by design. The benefit of this study, which identifies potentially eligible patients from parent clinical studies, allows for the continued access of durvalumab and observation of patients treated with durvalumab. Durvalumab will be provided to eligible, treatment-experienced patients who have been treated for months under parent clinical studies and have demonstrated a response and tolerability to treatment. They will be treated as long as they continue to receive benefit for treatment with durvalumab.

Conducting this study serves the important purpose to better understand the long-term patient safety and survival outcomes across a diverse group of patient population exposed to durvalumab.

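### Exclusion 14 is worded the wrong way round in both the protocol and the SAP, and exclusion 7 does not say whether it covers immune events caused by durvalumab

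*Protocol*

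**What the plan says.** The exclusion list in protocol section 5.2 opens with "Patients must not enter the study if any of the following key exclusion criteria are fulfilled", so a criterion that is met keeps the patient out. Items 2 to 15 apply to Cohorts 1 and 2 only.

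- **Exclusion 14** begins "Must not have required the use of additional immunosuppression other than corticosteroids for the management of an AE >Grade 1". It goes on, also in the negative, to recurrence of an AE on re-challenge and to a current need for more than 10 mg/day of prednisone or equivalent.
- **Exclusion 7** bars "Active or prior documented autoimmune or inflammatory disorders". Its list of examples includes sarcoidosis and ends with "rheumatoid arthritis, hypophysitis, uveitis, etc]). The following are exceptions to this criterion", after which exceptions (a) to (e) follow.
- **Exclusion 3** bars a patient who "Experienced an immune-mediated or non-immune-mediated (hematologic and non-hematologic) toxicity that led to permanent discontinuation of durvalumab" in the parent study.
- **Exclusion 4** bars unresolved toxicity of Grade 2 or higher "from previous anticancer therapy with the exception of alopecia, vitiligo, and the laboratory values defined in the inclusion criteria".

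Section 5 allows no waivers of entry criteria. SAP 2.2 repeats exclusions 7 and 14 with the same polarity under Deviation 1 and treats a patient who meets any listed exclusion as having a deviation.

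**The concern.** Exclusion 14 is an operative safety rule, and its literal meaning is the opposite of what it is for. A site that applied it as printed would turn away patients with no history of difficult immune toxicity and would not be stopped by this item from dosing someone on high maintenance steroids. A programmer or reviewer who applied the SAP copy as printed would flag compliant patients as deviators.

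Exclusion 7 raises a question of scope. Every candidate for Cohort 1 or 2 has already had durvalumab, so a prior inflammatory disorder on record may be a drug effect. The criterion sets no limit by cause or by onset relative to durvalumab. Under a literal reading, a patient who is benefiting and whose immune event is controlled could be refused dosing, although one aim in section 2.1 is "To provide continued access to durvalumab monotherapy until confirmed progressive disease (PD) to patients currently receiving treatment".

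**Working it through.** No figure in the plan bears on this point. The check is of wording and logic.

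**Exclusion 14.** Define A = needed immunosuppression beyond corticosteroids for an AE above Grade 1; B = an AE recurred on re-challenge; C = now needs more than 10 mg/day prednisone or equivalent. Three yes/no conditions give 2 × 2 × 2 = 8 combinations. The three negated clauses are joined by *and*, so the item is fulfilled only when not A, not B and not C all hold.

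| Patient | Combinations | As written | Evident intent |
|---|---|---|---|
| None of A, B, C | 1 | barred | not barred |
| At least one of A, B, C | 8 − 1 = 7 | not barred | barred |

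The two rules disagree in 1 + 7 = 8 of 8 combinations. If each clause is instead treated as a separate exclusion, the patient with none of the problems is still barred and the patient with all three is still let through. Neither literal reading works.

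**Exclusion 7 against the AESI list.** Section 8.3.13 gives hypophysitis, sarcoidosis and uveitis as events of special interest for durvalumab, and exclusion 7 lists all three. The exact count depends on how the brackets are read. Hypophysitis and uveitis are printed inside the bracket that follows Wegener syndrome, and colitis is printed as an example of inflammatory bowel disease. Strict bracketing leaves 1 condition (sarcoidosis). Treating the Wegener bracket as a slip in an open-ended list gives 3, and adding colitis gives 4. The conclusion needs only one.

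**Exceptions.** They cover (a) vitiligo or alopecia, (b) hypothyroidism stable on replacement, (c) chronic skin conditions needing no systemic therapy, (d) no active disease for 5 years, with Study Physician consultation, and (e) diet-controlled celiac disease. None of the 5 turns on drug causation or on onset relative to durvalumab, and none reaches a recent hypophysitis, uveitis or sarcoidosis.

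**Worked case.** A Cohort 1 candidate is benefiting. Uveitis in the parent study resolved on corticosteroids, durvalumab was not permanently stopped, and the event did not recur.

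- Exclusion 3: not met, because there was no permanent discontinuation.
- Exclusion 4: not met, because the event has resolved.
- Exclusion 14 in its intended sense: not met, because A, B and C are all absent.
- Exclusion 7 read literally: met, with no exception available.

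The patient is refused on exclusion 7 alone. Section 6.1.3, which governs restart and treatment through progression, bars toxicity that required permanent discontinuation and significant, unacceptable or irreversible toxicity. It also requires sections 5.1 and 5.2 to be met again, so the exclusion 7 question returns at that point.

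**The case against.** **Intent is clear for exclusion 14.** No site could run the trial on the literal wording, and the 8 of 8 result is what negating a rule always produces; it does not measure impact. SAP 2.2 has the medical team review and categorize deviations and uses WAVE data only, so false flags would probably be caught. All of this stands. It limits the consequence but does not make the text right.

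**Exclusion 7 probably means pre-existing disease.** Its list includes Graves' disease and rheumatoid arthritis. The protocol uses different terms for drug effects (toxicity in exclusions 3 and 4, AE in 14, AESI in 8.3.13). If exclusion 7 already barred every prior immune-mediated event, much of exclusions 3 and 14 would be redundant. This is the better reading, but the document does not state it, and a site with no power to waive has reason to follow the literal text.

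**Access was always conditional.** Section 1 offers continued treatment to eligible patients, and section 2.3.1 describes patients who "have demonstrated a response and tolerability to treatment". A cautious exclusion is the sponsor's choice. That also stands.

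A reader might infer that exclusion 7 contradicts exclusions 3, 4 and 14. It does not: the criteria are cumulative, and a broad bar can sit beside narrower ones. A reader might also infer that refused patients lose durvalumab altogether. The documents do not say whether the parent study could go on supplying it.

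**Conclusion.** Exclusion 14 is wrong as written in both documents and should be corrected. The correction rests on no assumption beyond its evident purpose. Exclusion 7 is a secondary point: its scope for treatment-caused events is unstated, the likely intent is pre-existing autoimmune disease, and a clarifying sentence is enough.

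The documents give no rate of prior immune-mediated events, so the number of patients affected cannot be estimated. Cohort 3 is unaffected. The effect on the deviation listing should be small after medical review. It would be tempting to conclude that sites enrolled patients on different rules, or that adverse event rates or endpoints are distorted. Nothing in the documents shows either, and neither is claimed.

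**What to change.** 1. **Exclusion 14**, in protocol 5.2 and SAP 2.2 Deviation 1, should state what excludes: *Needed immunosuppression beyond corticosteroids to manage an AE >Grade 1, or had an AE recur on re-challenge, or currently needs more than 10 mg/day of prednisone or equivalent as maintenance.*
2. **Exclusion 7**, in both places, should gain one sentence: *This criterion does not apply to immune-mediated events attributed to parent-study or WAVE treatment, which are governed by exclusions 3, 4 and 14 and by section 6.1.3, after consultation with the Study Physician.*

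The reference to 6.1.3 matters for Cohort 2. An immune event that arises after dosing was completed discontinued nothing, so exclusion 3 misses it, but the toxicity conditions in 6.1.3 apply at restart. The eligibility re-check in 6.1.3 works by reference and needs no edit.

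The cost is one reworded sentence and one added sentence in the protocol, with matching SAP lines. There are no new visits or procedures, and Study Physician consultation is already used in exception (d). The downside is that some patients with a prior controlled immune-mediated event will be dosed, under the existing safeguards in 6.1.3, 7.1 and Annex 1. Annex 1 is not among the documents reviewed.
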